Generally, the results of exercise programs show the final changes after an intervention, leaving aside the capacity for adaptation to workload during the intervention. The processes of adaptation to exercise are studied mainly in athletes; however, little is known about the adaptability capacity, in special populations, regarding CRFs, metabolic flexibility, physical function, and non-oncologic chronic pain, specifically in users belonging to the Cardiovascular Health Program of the External CESFAM of Valdivia, subjected to two types of exercise.

Despite knowing the link between non-oncologic chronic pain and the presence of cardiovascular diseases, the individual relationship between different cardiovascular risk factors and pain intensity is still uncertain.

Thus, implementing a physical exercise program associated with the PSCV will improve the possibility of controlling CRFs, improving metabolic flexibility, reducing non-oncologic chronic pain, and promoting lifestyle change difficult to achieve in users of this cohort. On the other hand, the External CESFAM will be recognized as a pioneering establishment in the implementation of non-pharmacological alternatives (personalized and expert-guided physical exercise) to improve the health and quality of life of PSCV users, which will not generate extra costs to the establishment for its application.

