## **Objectives**

### **General**

- Objective 1: Evaluate the effects of a 12-week HIIT and ERE program on the workload adaptation capacity in cardiometabolic risk factors, physical function, and non-oncologic chronic pain in users of the Cardiovascular Health Program at the External CESFAM of Valdivia.
- Objective 2: Determine the relationship between cardiovascular risk factors and non-oncologic chronic pain in users of the Cardiovascular Health Program at the External CESFAM of Valdivia.

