## **Specific**

- Objective 1.1: Analyze the effects of a 12-week HIIT and ERE program on the workload adaptation capacity in cardiometabolic risk factors, physical function, and non-oncologic chronic pain in users of the Cardiovascular Health Program at the External CESFAM of Valdivia.
- Objective 1.2: Compare the effects of a 12-week HIIT and ERE program on the workload adaptation capacity in cardiometabolic risk factors, physical function, and non-oncologic chronic pain in users of the Cardiovascular Health Program at the External CESFAM of Valdivia.
- Objective 2.1: Determine the relationship between the number of cardiovascular risk factors and the presence of non-oncologic chronic pain in users of the PSCV at the External CESFAM of Valdivia.
- Objective 2.2: Determine the relationship between the number of cardiovascular risk factors and the intensity of non-oncologic chronic pain in users of the PSCV at the External CESFAM of Valdivia.
- Objective 2.3: Associate the presence of non-oncologic chronic pain with other chronic diseases.

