### **Data Collection Techniques and Instruments**

Clinical Record Information Collection The following information will be obtained from each participant's clinical record:

- Sociodemographic Background: o Gender o Age o Ancestry o Education
- Medical Background o Time within the cardiovascular health program o Morbid history o Medications and dosage o Time using medications o Laboratory tests (fasting glucose, glycosylated hemoglobin, lipid profile)

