## **High-Intensity Interval Training (HIIT)**

During HIIT, 8-10 intervals/session will be performed on a cycle ergometer, at an intensity of 80-100% of the theoretical maximum heart rate (MHR) according to Karvonen, equating to a bicycle load of 8 to 10 points on the modified Borg scale of 1-10 points (55). Each interval will consist of 1 minute of cycling, followed by 2 minutes of inactive rest, similar to previous protocols (27). Every two weeks, the bicycle load will be adjusted (increasing the resistance to pedaling of the bicycle) due to normal physiological adaptations and improvement of the patient's baseline threshold, always exercising the patient in each effort interval at a muscular intensity of 8 to 10 points according to the modified Borg scale similar to previous studies (27).

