## **Statistical Analysis**

The sample size will be calculated as follows: (1) ANOVA for repeated measures with intra-inter-group interaction, (2) three groups, (3) type I error: 5%, (4) type II error: 20%, (5) statistical test power: 80%, and (6) effect size (ES): 0.10 according to Cohen's classification (1988). Using these parameters, the total sample size recommended by G\*Power software (Version 3.1.9.2) was 174 (58 per group). Assuming a 10% dropout, the total was calculated at 192, with 64 participants randomly assigned to each group. The concealment of allocation will be conducted by a researcher not involved in the clinical procedures of the intervention using the

method of opaque, sealed, and consecutively numbered envelopes. The random sequence and allocation concealment allow for the control of selection bias.

For enhanced bias control, the data analysis will be performed by a researcher blinded to the intervention groups. Dependent variables will be described in terms of mean and standard deviation. Assumptions of normality and homoscedasticity for all data will be verified using the Shapiro-Wilk test and the Levene's test, respectively. To address General Objective 1, the Student's t-test will be used to detect baseline differences between groups, and a repeated measures ANOVA (group x time) to determine differences in all dependent variables between training prior, and at 4, 8, and 12 weeks afterwards. The Bonferroni post hoc test will be used to test differences between groups. Additionally, the Cohen's d test will be applied to determine the effect size. To address the General Objective, the Pearson correlation test will be used to determine the relationship between MHR and the presence and intensity of non-oncological chronic pain. The level for statistical significance was set at  $p < 0.05$ . Statistical analyses will be performed using SPSS software version 21 (SPSS™ Inc., Chicago, IL, USA).

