## **Expected Results**

Following the training application, we expect that the measured variables will modify their values on average in favor of greater adaptation to workloads, improved health condition, better quality of life, and a reduction in the pharmacological arsenal used before the intervention. Additionally, implementing a physical exercise program associated with the PSCV will improve the possibilities of controlling MHR and promote lifestyle changes in users of this population. Moreover, the CESFAM Externo will be showcased as a pioneering establishment in the implementation of non-pharmacological alternatives (personalized physical exercise and guided by experts in physical exercise and health) to improve the health and quality of life of PSCV users, which will not generate extra expenses for its application. On another front, the results obtained during the intervention could be published in press articles, congresses, and scientific journals to disseminate the good practices carried out by CESFAM and the Universidad San Sebastián.

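### Objective 2 is analysed by an unadjusted Pearson correlation with a mislabelled predictor, so a reported link between risk factors and pain could reflect age alone

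*Combined protocol and SAP*

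**What the plan says.** General Objective 2 is to "Determine the relationship between cardiovascular risk factors and non-oncologic chronic pain". Under the specific objectives, 2.1 is to "Determine the relationship between the number of cardiovascular risk factors and the presence of non-oncologic chronic pain" and 2.2 is to "Determine the relationship between the number of cardiovascular risk factors and the intensity of non-oncologic chronic pain". Objective 2.3 links the presence of pain to other chronic diseases.

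One sentence in Statistical Analysis serves all of this: "the Pearson correlation test will be used to determine the relationship between MHR and the presence and intensity of non-oncological chronic pain". It is introduced as addressing the General Objective, without a number; its content shows that Objective 2 is meant. No covariate, regression, partial correlation or stratification is named there or anywhere else, and Objective 2.3 has no analysis assigned by name.

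The only definition of the predictor is in the HIIT section: "theoretical maximum heart rate (MHR) according to Karvonen". Expected Results uses the same abbreviation differently, saying that the programme "will improve the possibilities of controlling MHR". That makes sense only if risk factors are meant.

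Data Collection Techniques and Instruments lists "Sociodemographic Background: o Gender o Age o Ancestry o Education", together with morbid history and medications. The Problem Statement gives the motivation: "the individual relationship between different cardiovascular risk factors and pain intensity is still uncertain".

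**The concern.** Age plausibly drives both the number of risk factors a person carries and whether, or how badly, that person has chronic pain. The population is adult programme users, and no upper age limit is stated. A bivariate correlation cannot tell a risk-factor relationship from a shared dependence on age. The results are intended for publication with a 0.05 threshold, so a significant r would readily be read as a finding about risk factors.

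Two lesser problems accompany this. The outcome of Objective 2.1 is yes/no, and a correlation coefficient with a yes/no variable gives no odds ratio or risk difference that a clinic could use. A count also cannot say which factor matters, whereas the stated motivation concerns the factors individually.

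**Working it through.** **The plan's own figure.** The sample size was set for Objective 1 only. With f = 0.10, 3 groups, 4 visits, and correlation 0.5 and sphericity 1 (both assumed, since neither is stated), the noncentrality is 0.10² × 174 × 4 / (1 − 0.5) = 13.92 on 6 and 513 degrees of freedom. Power is 0.804, so 174 is reproduced. Then 174 × 1.10 = 191.4, giving 192. No target correlation or power is given for Objective 2. At n = 192 the smallest significant |r| is tanh(1.96/√189) = 0.142, and the |r| detectable with 80% power is about 0.20.

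**Inputs for the age check.** n = 192 (Statistical Analysis). Two-sided 0.05 (sidedness assumed). Pain prevalence 32.1%, the national figure in the Problem Statement, assumed here for programme users. Age correlations are assumed and varied from 0.1 to 0.5, because the documents give none. Given age, the count and pain are independent.

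**Formula.** If age correlates a with the count and b with pain on a continuous scale, the induced correlation is a × b. For yes/no pain it shrinks by φ(z)/√(p(1 − p)), which is 0.767 at p = 0.321. The chance of significance is Φ(δ − 1.96) + Φ(−δ − 1.96), with δ = arctanh(r) × √189.

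Worked case, a = b = 0.3, pain presence: r = 0.09 × 0.767 = 0.069; δ = 0.069 × 13.75 = 0.95; Φ(−1.01) + Φ(−2.91) = 0.156 + 0.002 = 16%.

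| a = b | Induced r, presence | Significant, formula | Significant, simulated | Induced r, intensity | Significant, intensity |
|---|---|---|---|---|---|
| 0.1 | 0.008 | 5% | 6% | 0.01 | 5% |
| 0.2 | 0.031 | 7% | 8% | 0.04 | 8% |
| 0.3 | 0.069 | 16% | 16% | 0.09 | 24% |
| 0.4 | 0.123 | 40% | 40% | 0.16 | 61% |
| 0.5 | 0.192 | 76% | 74% | 0.25 | 94% |

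Adjusting for age brings the rate to about 5% in every setting, by logistic regression for presence and by partial correlation for intensity. Scoring the count in different ways moves the presence figures a little: about 14% to 16% at 0.3 and 36% to 40% at 0.4. The product a × b is what matters. With 0.1 and 0.5, the intensity figure is only about 11%.

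**Count against individual factors.** This is an illustration with a continuous outcome, n = 192, and four independent factors at 40% prevalence each.

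| True effects | Count correlation significant | First factor's own term significant |
|---|---|---|
| One factor, 0.5 SD | 38% | 92% |
| Two factors, opposite, 0.5 SD each | 5% | 92% |
| All four, 0.25 SD each | 92% | 38% |

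Neither form is better throughout; they answer different questions.

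**Model size.** Expected pain cases: 0.321 × 192 = 61.6, about 62. At ten cases per term that is about six terms, exactly what four factors plus age and sex use.

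**The case against.** The strongest reply is that the plan asks for a relationship, and Pearson tests marginal association. In the scenarios above the count and pain really are associated, through age, so a significant result is correct for the question as worded. This stands. The percentages are not the type I error of the planned test; they are the chance of a significant result when there is no relation beyond age.

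Several stronger readings are tempting, and the documents do not support them:

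- **The method collapses everything to one summary variable.** That is inferred from Objectives 2.1 and 2.2. Statistical Analysis names MHR, which could stand for several factors correlated one by one. The lack of adjustment would remain.
- **Using a count is an error.** It is what Objectives 2.1 and 2.2 ask for. The mismatch is with the motivation in the Problem Statement.
- **Pearson is invalid for yes/no pain because r cannot exceed about 0.77.** With a binary variable it is equivalent to a two-sample t-test, and the cap lies far above the detectable 0.20. Only the lack of a usable effect measure survives.
- **The plan really correlates maximum heart rate with pain.** Expected Results points to a labelling slip. If it were literal and MHR were computed linearly from age (an assumption), the predictor would carry only age information, and adjusting for age would be impossible.

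**Conclusion.** The point holds in limited form. Objective 2 rests on one unadjusted correlation with a mislabelled predictor, and age and gender are collected but not used. An association reported from it could be age alone. A reader might infer that it will be; the documents do not show that. The size depends on correlations they do not give. At 0.1 to 0.2 the effect is negligible to small (about 6% to 8% for presence). From about 0.3 it is material (16%, then 40% and 74%), and it is larger for intensity (24%, 61%, 94%). The presence figures also assume the national prevalence. Objective 1 and its sample size are unaffected. The change should be made because Objective 2 is one of two general objectives and the data needed are already collected.

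**What to change.** In Statistical Analysis, replace MHR with the number of cardiovascular risk factors, list the factors counted, and state that week-0 data are used. Then specify:

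- **Objective 2.1:** logistic regression of pain presence on the count, adjusted for age and sex, reporting odds ratios with 95% confidence intervals.
- **Objective 2.2:** linear or ordinal regression of pain intensity on the count, adjusted for age and sex.
- **Secondary, for the question in the Problem Statement:** both models refitted with hypertension, diabetes, dyslipidaemia and obesity in place of the count. State that about 62 pain cases, if prevalence is 32%, only just support the six terms of the presence model. Physical inactivity is an entry criterion and cannot be a term.
- **Objective 2.3:** logistic regression of pain presence on the other chronic diseases in the morbid history, adjusted for age and sex.

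The cost is a paragraph of plan text and regressions on variables already collected. The downside is a few degrees of freedom and slightly wider intervals.

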## **Expected Results**

Following the training application, we expect that the measured variables will modify their values on average in favor of greater adaptation to workloads, improved health condition, better quality of life, and a reduction in the pharmacological arsenal used before the intervention. Additionally, implementing a physical exercise program associated with the PSCV will improve the possibilities of controlling MHR and promote lifestyle changes in users of this population. Moreover, the CESFAM Externo will be showcased as a pioneering establishment in the implementation of non-pharmacological alternatives (personalized physical exercise and guided by experts in physical exercise and health) to improve the health and quality of life of PSCV users, which will not generate extra expenses for its application. On another front, the results obtained during the intervention could be published in press articles, congresses, and scientific journals to disseminate the good practices carried out by CESFAM and the Universidad San Sebastián.

## **Work Plan (Gantt Chart)**

### **Month 1**

- Logistical meeting and coordination with the head of the Cardiovascular Health Program and Director.
- Presentation of the project to the Scientific Ethics Committee

## **Month 2**

- Patient eligibility process o Contact from CESFAM to eligible users o On-site recruitment at CESFAM Externo or invitation to the project by phone call o Signing of informed consent o Collection of sociodemographic information

## **Month 3**

- Pre-intervention evaluation (IPAQ, SF36, Cardiometabolic Variables, Metabolic Flexibility, and Pain)
- Exercise familiarization

## **Months 4, 5, and 6**

- Application of training protocols
- Evaluation of workload adaptation every 4 weeks, until week 12 (Cardiometabolic Variables, Pain).

## **Month 7**

- Tabulation of results in Excel spreadsheets
- Delivery of preliminary results to CESFAM Externo.
- Time for unforeseen events in the application of the protocol

